8.2.1 Relationship to Study Drugs

The investigator will use the following definitions to assess the relationship of the AE to the use of rovalpituzumab tesirine, nivolumab, or ipilimumab:

Reasonable Possibility After consideration of factors including timing of the event, biologic plausibility, clinical judgment, and potential alternative causes, there is **sufficient** evidence (information) to suggest a causal relationship.

No Reasonable Possibility After consideration of factors including timing of the event, biologic plausibility, clinical judgment, and potential alternative causes, there is **insufficient** evidence (information) to suggest a causal relationship.

For causality assessments, events assessed as having a reasonable possibility of being related to the study drug will be considered “associated.” Events assessed as having no reasonable possibility of being related to study drug will be considered “not associated.” In addition, when the investigator has not reported a causality or deemed it not assessable, AbbVie will consider the event associated.

If an investigator’s opinion of no reasonable possibility of being related to study drug is given, another cause of event must be provided by the investigator for the SAE.

8.2.2 Deaths

For SAEs with the outcome of death, the date and cause of death will be recorded on the appropriate case report form.

Deaths that occur during the protocol specified AE reporting period that are more likely related to disease progression will therefore be considered as expected AE and will not be subject to expedited reporting.

Death should be considered an outcome and not a distinct event. The event or condition that caused or contributed to the fatal outcome should be recorded as the single medical concept on the AE eCRF. Generally, only one such event should be reported. The term "sudden death" should only be used for the occurrence of an abrupt and unexpected death due to presumed cardiac causes in a subject with or without pre-existing heart disease, within 1 hour of the onset of acute symptoms or, in the case of an unwitnessed death, within 24 hours after the subject was last seen alive and stable. If the cause of death is unknown and cannot be ascertained at the time of reporting, "unexplained death" should be recorded on the AE eCRF. If the cause of death later

becomes available (e.g., after autopsy), "unexplained death" should be replaced by the established cause of death.

8.2.2.1 Eliciting Adverse Events

An open-ended or non-directed method of questioning should be used at each study visit to elicit the reporting of AEs.

8.2.2.2 Recording Adverse Events

The following information should be recorded on the AEs and medical history eCRF:

- Description using standard medical terminology, including any onset and resolution dates
- Whether the AE met serious criteria
- Grade or Severity
- Relationship to study drug(s) or alternate causality
- Outcome

8.2.2.3 Diagnosis vs. Signs or Symptoms

In general, the use of a unifying diagnosis is preferred to the listing of individual symptoms. Grouping of symptoms into a diagnosis should only be done if each component sign and/or symptom is a medically confirmed component of a diagnosis as evidenced by standard medical practice. If any aspect of a sign or symptom does not fit into a classic pattern of the diagnosis, the individual symptom should be reported as a separate AE.

For infusion-related reactions, if multiple signs or symptoms occur with a given infusion-related event, each sign or symptom may be recorded separately with its own level of severity.

8.2.2.4 Recording Serious Adverse Events

For SAEs, record the event(s) on both the eCRF and an SAE form.

The following should be considered when recording SAEs:

- Death is an outcome of an event. The event that resulted in the death should be recorded and reported on both the SAE form and the eCRF.
- For hospitalizations, surgical or diagnostic procedures, the illness leading to the surgical or diagnostic procedure should be recorded as the SAE, not the procedure itself. The procedure should be captured in the narrative as part of the therapeutic action taken in response to the illness.

8.2.2.5 Adverse Events Expected Due to SCLC or Progression of SCLC

AEs that may be expected from primary SCLC lesions, compression of adjacent thoracic structures or distant metastases are presented in Appendix 13.10, Adverse Events Expected Due to SCLC or Progression of SCLC of the protocol.

These AEs may occur alone or in various combinations and are considered expected AEs in SCLC subjects.

The term “disease progression” alone should not be used when reporting AEs or SAEs, due to its lack of specificity. Rather, symptoms of disease progression should be collected under the unifying diagnosis of "malignant neoplasm progression"; symptoms of progression may be subsumed under this diagnosis.

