1.2 Delta-like Protein 3 and Rovalpituzumab Tesirine

Delta-like protein 3 (DLL3) is an inhibitory ligand of the Notch receptor family. It is highly expressed in high-grade tumors of neuroendocrine origin such as SCLC, including its tumor perpetuating cells (TPCs), but with no detectable surface protein expression in normal tissues or non-neuroendocrine tumor (NET) types (Saunders, 2015; AbbVie data on file). While the function of DLL3 has not been clearly defined, it has been implicated in the regulation of cell development and fate decisions (Dunwoodie, 1997; Chapman, 2011).

Rovalpituzumab tesirine (SC16LD6.5) is a DLL3-targeted antibody-drug conjugate (ADC) consisting of the humanized DLL3-specific IgG1 monoclonal antibody SC16; the DNA cross-linking agent SC-DR002 (D6.5); and a protease-cleavable linker that covalently links SC-DR002 to SC16. The primary mechanism of rovalpituzumab tesirine is binding of the ADC to DLL3 on target-expressing cells, followed by internalization of the ADC-DLL3 complex and release of SC-DR002 via proteolytic cleavage in late endosomes. Interstrand crosslinks of cellular DNA induced by intercalated SC-DR002 leads to cellular cytotoxicity.

In a Phase 1 study (SCRX16-001), rovalpituzumab tesirine exhibited encouraging efficacy in recurrent SCLC, achieving a 31% (8/26) and 85% (22/26) central review-adjudicated confirmed objective response rate (ORR) and clinical benefit rate (CBR) (39% [10/26] and 73% [19/26] by investigator review), respectively, in DLL3 \geq 50% tumors dosed at 0.2-0.4 mg/kg. Median overall survival (OS) was 7.7 months in DLL3 \geq 50% subjects at all dose levels, with a 1-year survival rate of 30%. In DLL3 \geq 50% tumors in the third line setting, rovalpituzumab tesirine achieved a 33% (4/12) and 83% (10/12) central review-adjudicated confirmed ORR and CBR, respectively, with a median survival of 5.8 months and a 1-year survival rate of 37%.

Rovalpituzumab tesirine was generally tolerated, with the most common Grade 3 or higher AEs of serosal effusions and thrombocytopenia occurring in 14% and 12% of subjects, respectively (AbbVie data on file). Therefore, rovalpituzumab tesirine appears to be an active anticancer therapy.

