1.4 Rationale for the Study and Anticipated Risks

Although rovalpituzumab tesirine as well as the checkpoint inhibitors nivolumab and ipilimumab have demonstrated encouraging efficacy in SCLC, neither approach alone appears at this time sufficient to afford a complete clinical benefit or cure in the majority of patients, where medical need remains high. Their mechanisms of actions are complementary and toxicities generally non-overlapping, though, suggesting that combination therapy may be safe, and clinical benefit may be additive or even synergistic. Indeed, preliminary studies indicate that ADCs like rovalpituzumab tesirine may, at least in part, result in immunogenic cell death of tumors, complementing the immuno-regulatory effects of checkpoint inhibitors like nivolumab and/or ipilimumab (Gerber, 2016). However, no formal clinical studies have previously examined the tolerability of rovalpituzumab tesirine administered in combination with checkpoint inhibitors. This study will therefore explore the safety, tolerability, and antitumor activity of rovalpituzumab tesirine administered in combination with nivolumab with or without ipilimumab. Upon completion of the study, decisions to further advance this program will also include review of the ORR rate. The lower bound value of the 95% confidence interval for the ORR rate observed will be compared to the ORR rate of 23% and used as one of the factors in making the decision.

The most frequent treatment-emergent adverse event (TEAE) terms considered related to rovalpituzumab tesirine have included fatigue (35%), peripheral edema (23%), and nausea (19%), while the most frequent, related TEAEs of Grade 3 or higher have included serosal effusions (14%), thrombocytopenia (12%), and skin reactions (8%). In addition, preclinical toxicology studies conducted in the rat and the cynomolgus monkey have identified the bone marrow, lung and kidney as a potential source of clinical AEs (AbbVie data on file).

Warnings for nivolumab include immune-mediated reactions, including pneumonitis, colitis, hepatitis, endocrinopathies, nephritis, rash, and encephalitis, as well as infusion reactions and embryo-fetal toxicity. The most common adverse reactions ($\geq 20\%$) in patients with melanoma were fatigue, rash, musculoskeletal and back pain, pruritus, diarrhea, upper respiratory tract

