3.1.1 Definition of Dose-Limiting Toxicities

The DLT evaluation period is the first 12 weeks of treatment for all subjects. DLTs are defined as any of the following in the DLT-evaluation period, graded according to the National Cancer Institute's Common Terminology Criteria for Adverse Events (NCI CTCAE), version 4.03 (see Appendix 13.6)

- Grade 4 thrombocytopenia (or Grade 3 thrombocytopenia with bleeding) lasting more than 7 days and/or requiring platelet transfusion
- Grade 4 neutropenia lasting more than 7 days, and/or requiring hematopoietic growth factor rescue, or any febrile neutropenia (Grade 3 or 4 neutropenia with concurrent fever $\geq 38.3^{\circ}\text{C}$)
- Grade 4 anemia unrelated to underlying disease

- Clinically-significant Grade 3 or 4 non-hematologic laboratory abnormality that does not resolve to Grade 0/1 or baseline within 7 days
- Grade 3 or 4 non-laboratory AE with the exception of fatigue, asthenia, nausea, or other manageable constitutional symptom

The following events will not be considered DLTs:

- Any AE \geq Grade 3 clearly determined to be unrelated to study drug(s) (e.g., disease progression)
- \geq Grade 3 isolated alkaline phosphatase, amylase, or lipase laboratory abnormality of any duration
- \geq Grade 3 endocrinopathies controlled by hormone replacement
- Grade 3-4 electrolyte abnormalities

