8.3.1 Management of Serosal Effusions/Serositis

Serosal effusions (pleural or pericardial, or ascites) have been observed with rovalpituzumab tesirine, and have the potential to be life-threatening (e.g. pericardial tamponade). Therefore, development of any of these events or worsening from baseline warrants prompt evaluation by the investigator or designee. Alternative causes, such as infection, congestive heart failure, disease progression, and in particular an immune-mediated AE (as might be caused by a checkpoint inhibitor; see Section 8.3.3), should be ruled out. When appropriate, a unifying

diagnosis should be reported, e.g. "heart failure," not simply "pleural effusion" and "edema limbs."

When considered clinically significant (e.g. grade 2 or higher and considered related to study drug):

- Systemic corticosteroids, when initiated promptly, have been reported to be beneficial in some prior cases during treatment with rovalpituzumab tesirine. The investigator should consider initiation of prednisone 1-2 mg/kg/day or equivalent, initiating a taper after improvement to Grade 1 or less, over the following 2-4 weeks.
- Until clinical experience suggests otherwise, guidance for dose delay and/or reduction of rovalpituzumab tesirine, as well as criteria for ongoing dosing, should follow Section 5.2.3 and Section 5.5.

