13.10 Adverse Events Expected Due to SCLC or Progression of SCLC

Preferred Term
Pleural effusion
Malignant pleural effusion
Metastases to pleura
Dyspnoea
Cough
Non-cardiac chest pain
Haemoptysis*
Oesophageal obstruction
Pneumonia*
Vocal cord paralysis
Dysphonia
Dysphagia
Superior vena cava syndrome
Horner's syndrome
Metastases to bone
Metastases to lymph nodes
Metastases to liver
Metastases to spine
Metastases to the mediastinum
Metastases to pleura
Metastases to adrenals
Metastases to meninges
Metastases to central nervous system
Metastatic pain
Cancer pain
Tumour pain
Fatigue
Asthenia
Pulmonary embolism*
Shock*
Septic shock*
Deep vein thrombosis*
Lower respiratory tract infection*
Respiratory tract infection*
Upper respiratory tract infection*
Opportunistic infection*
Viral infection*
Fungal infection*
Bacterial infection*
Pulmonary haemorrhage*

Preferred Term
Lung abscess*
Empyema*
Sepsis*
Lymphadenopathy
Decreased appetite
Malaise
Weight decreased
Headache
Pain excluding chest pain
Pyrexia

*Includes life-threatening or fatal events.

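### An effusion attributed to progression or to a unifying diagnosis can lose its own graded adverse event term, and one attributed to progression can also leave the DLT count

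*Combined protocol and SAP*

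**What the plan says.** Section 1.2 describes the "most common Grade 3 or higher AEs of serosal effusions and thrombocytopenia occurring in 14% and 12% of subjects, respectively". Section 1.4 repeats 14% for related Grade 3+ events, with serosal effusions ranked first. Section 8.3.1 defines the group: "Serosal effusions (pleural or pericardial, or ascites) have been observed with rovalpituzumab tesirine".

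Three provisions decide how such an event is recorded and counted.

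- **Section 8.2.2.5** collects symptoms of disease progression under one term, malignant neoplasm progression, and adds that "symptoms of progression may be subsumed under this diagnosis". It points to Appendix 13.10, whose list of events expected from SCLC opens with "Pleural effusion" and "Malignant pleural effusion".
- **Section 8.3.1** asks for prompt evaluation and for other causes, progression among them, to be ruled out. It also says that, when appropriate, a unifying diagnosis should be reported and not merely the effusion; its example is heart failure.
- **Section 3.1.1** makes a DLT of any "Grade 3 or 4 non-laboratory AE with the exception of fatigue, asthenia, nausea, or other manageable constitutional symptom", so a Grade 3 or 4 effusion qualifies. It then exempts Grade 3+ events "clearly determined to be unrelated to study drug(s) (e.g., disease progression".

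Section 10.3.5.1 plans MedDRA-coded TEAE incidence by cohort. Section 10 names no grouped effusion term. Under Section 3.1, at most 1 DLT among 6 evaluable subjects permits enrollment beyond 12.

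**The concern.** Safety is the primary objective and there is no control arm, so no comparison would show a shortfall in effusions. A pleural effusion in SCLC may come from the drug or from the tumor, and the choice is left to the investigator. If the investigator chooses progression, the site may enter only the progression term. An all-cause TEAE table protects against wrong attribution only when the event has a row of its own; it cannot recover a term that was never entered. The unifying-diagnosis sentence in Section 8.3.1 is a second way out of the effusion row.

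At stake are the reported rate and grade of the toxicity that the protocol itself ranks first and, for effusions called progression, a DLT count that rests on six subjects.

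**Working it through.** The plan gives no figure of its own on this point, so there is none to reproduce. The check has two parts.

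**1. Does any safeguard catch an effusion that the investigator firmly attributes to progression?**

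| Safeguard | What it does | Caught? |
|---|---|---|
| Section 8.2.2.3 | Allows grouping only when each sign is medically confirmed as part of the diagnosis | No. Appendix 13.10 presents pleural effusion as a recognised feature of SCLC, so the test is easily met |
| Section 3.1.1 | Exempts an event from DLT status only when unrelatedness is clear | No. The investigator regards it as clear; no criterion or adjudicator is named |
| Section 8.2.1 | Treats missing or non-assessable causality as associated | No. A causality has been given |
| Section 8.3.1 | Asks that progression be ruled out as a cause | No. It does not require a separate effusion term when progression remains the explanation |

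Section 7.2.2 has a central reader adjudicate tumor response, but Section 8.2.2.5 does not tie the progression adverse event term to that reading.

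**2. How much could it matter?**

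Inputs from the documents: 14% for Grade 3+ effusion (Sections 1.2 and 1.4), up to about 30 subjects per cohort (Section 10.1), and the rule of at most 1 DLT in 6 (Section 3.1).

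Assumptions not in the documents: 14% also applies within the 12-week DLT window; a fraction f of effusions is relabelled as progression; other DLTs occur independently at rate q.

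Expected Grade 3+ effusions tabulated in 30 subjects = 30 × 0.14 × (1 − f):

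- f = 0: 4.2
- f = 0.5: 2.1 (an apparent rate of 7%)
- f = 1: 0

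Counted DLT rate: p = 1 − [1 − 0.14(1 − f)](1 − q).

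Probability of meeting the rule: P(X ≤ 1) = (1 − p)^6 + 6p(1 − p)^5.

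Example with q = 0.10 and f = 0: p = 1 − 0.86 × 0.90 = 0.226, and P = 0.774^6 + 6 × 0.226 × 0.774^5 = 0.215 + 0.377 = 0.59.

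| Other DLT rate q | f = 0 | f = 0.5 | f = 1 |
|---|---|---|---|
| 0 | 0.80 | 0.94 | 1.00 |
| 0.10 | 0.59 | 0.75 | 0.89 |
| 0.20 | 0.39 | 0.52 | 0.66 |
| 0.30 | 0.24 | 0.32 | 0.42 |

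The f = 1 column is an extreme: it needs every effusion, including pericardial effusion and ascites, to be called progression. If only pleural events are relabelled, f cannot exceed the pleural share of the 14%, which the documents do not give.

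One comparison needs no assumed rate. If two of six subjects have DLTs and one of these is an effusion relabelled as progression, 2/6 becomes 1/6 and the criterion for expansion is met.

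**The case against.** The strongest reply is that the protocol already limits this. Section 8.2.2.5 says *may*, and applies only to symptoms of progression. Section 8.2.2.3 sends anything that does not fit the usual pattern of the diagnosis to a separate event. An effusion of doubtful origin is not clearly unrelated, so under Section 3.1.1 it stays a DLT. Effusions are also looked for by echocardiogram (Section 7.7.5), by the redosing criteria (Section 5.2.3), by the fluid questionnaire (Section 7.7.7) and on serial CT. The SMC reviews safety at each cohort step, and at 1/6 or fewer expansion is permitted, not automatic.

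Most of this stands. Read together, these sections keep the doubtful effusion in the data; what they miss is the effusion that is wrongly but confidently called progression. The other assessments inform care and SMC review, but none produces a graded count of all serosal effusions.

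A reader might infer three stronger things that the documents do not support.

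- **That the Appendix 13.10 listing removes effusions from the tables or the DLT count.** It does not. Listed events are still adverse events, and nothing exempts them from collection, tabulation or DLT assessment. The list names only pleural terms, not pericardial effusion or ascites.
- **That following the recording rule necessarily biases the effusion rate downward.** A drug-caused effusion is lost only if it is misattributed or replaced by another diagnosis. Even then the event appears as a TEAE under the other term; what disappears is the effusion term and its grade.
- **That the 14% forecasts DLTs here.** It comes from earlier experience with the drug, has no denominator, covers all three effusion sites and is not tied to 12 weeks.

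Section 10 also defers further detail to the Statistical Analysis Plan. The reviewed file contains only the protocol's statistical section, so a separate plan could already include a grouped effusion table.

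**Conclusion.** The point holds as a possible bias in the primary safety data. The recording rules in Sections 8.2.2.5 and 8.3.1 allow the drug's leading Grade 3+ toxicity to be entered without its own term and grade. For effusions attributed to progression, Section 3.1.1 can also take them out of the DLT count. The unifying-diagnosis route affects the effusion row only; it does not by itself exempt the event from DLT status.

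The direction is toward fewer reported effusions, but the size cannot be fixed from the documents. With half of effusions relabelled, the chance of meeting the expansion criterion rises by 0.08 to 0.15 across the assumed other-DLT rates of 0 to 30% (for example, 0.32 − 0.24 and 0.75 − 0.59, from unrounded values 0.085 and 0.154). These figures depend on the assumptions stated with the calculation and are illustrations only. The firmer statement is that, with six evaluable subjects, one relabelled event can change the result. This does not undermine the design; it justifies an inexpensive clarification.

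**What to change.** 1. In Section 8.2.2.5, require every new or worsening pleural, pericardial or ascitic effusion to be recorded as its own graded adverse event, whatever its attribution, in addition to any unifying diagnosis. Make a matching edit to the unifying-diagnosis sentence in Section 8.3.1, so that the two sections do not conflict.
2. Prespecify a grouped serosal-effusion TEAE table (pleural, pericardial, ascites) by grade and cohort, regardless of causality. If a separate analysis plan already has one, a cross-reference is enough.
3. Have the existing SMC see any Grade 3+ effusion in the DLT window that was excluded as progression.

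Appendix 13.10 can stay as it is, because the listing does not affect tabulation.

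The cost is a wording change in two sections, matching eCRF guidance, one table and a short SMC listing. No dose or treatment rule changes. The downside is that some disease-related effusions will be counted, so the reported rate will look slightly less favourable; keeping the investigator's attribution beside each event lets readers see how many.

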8.2.2.6 Reporting Periods for Adverse Events and Serious Adverse Events

The safety reporting period for all AEs and SAEs is from the time of study drug administration (Cycle 1 Day 1) until 100 days following discontinuation of study drug administration. In addition, protocol related serious adverse events and protocol-related nonserious adverse events will be collected from the time the subject signed the study-specific informed consent, only if considered by the Investigator to be causally related to study-required procedures. All SAEs that occur after the safety reporting period and are considered study treatment-related in the opinion of the investigator should also be reported to the sponsor or designee.

Each SAE must be followed until the SAE returns to baseline (resolves or recovers to baseline) or the SAE stabilizes (resolves or recovers with sequelae); the SAE is considered not recovered or not resolved by the investigator; or the subject dies (the SAE end date is equal to the date of death). SAE outcome may not be possible to collect when a subject withdraws consent.

Additionally, all SAEs that occur *after* the safety reporting period (as defined above) that are considered study treatment-related by the investigator, should also be reported to the sponsor or its designee.

All non-serious AEs will be followed through the safety reporting period.

